**\* (2) Identify materials that will be used to recruit subjects (select all that apply):**

---

Letter, email, flyer, postcards, CD, DVD

---

Use of websites or Apps (e.g. Facebook, ResearchMatch)

---

Other

**\* Describe:**

Study team may also recruit participants via text message/phone.

**Statistical Analysis Plan:**

The primary analysis for all self report study outcomes is based on assessing mean differences across the two study arms. Our arms include rural residents who are assigned either to the general (group 1) or rural targeted (group 2) antibody video group. A series of independent samples t-tests were conducted for all interval level/self-report outcomes, which included Theory of Planned Behavior and rural-adapted anticipatory racism measures. We also computed Cohen's d effect sizes to consider practical significance of pairwise differences. Subsequent analyses will explore sociodemographic variables and individual differences, such as gender and rural identity, as potential moderators of group differences. Future exploratory considerations will utilize hierarchical moderated multiple regression procedures.

For dichotomous (yes-no) outcomes related to accepting and completing the antibody test kit we conducted two group chi square goodness of fit tests.

Please feel free to contact me at [[contact]](mailto:[contact]) with any questions.

Thank you,

[name]  
C.S. Mott Endowed Professor of Public Health  
Charles Stewart Mott Department of Public Health  
College of Human Medicine, Michigan State University

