## **2. \* Describe the subject population.**

This study will recruit both male and female participants who are Black/African-American or White/Caucasian and enrolled in the Flint Registry. All participants will be 18 and over. We aim to recruit a total sample size of 500 individuals. We will stratify by age and recruit even sample sizes of  $N = 167$  children 18-21, young adults 22-40; and older adults 40 and above (see Inclusion of Individuals Across the Lifespan). Each age group will be further stratified by race and gender. We will recruit a two-thirds African American sample ( $N = 110$ ), and a one-third White sample ( $N = 57$ ), both of which will be one-third to one-half male. The inclusion of both a one-third White sample and a one-third male sub-sample will ensure that we are able to conduct effective race and gender comparisons.

For the vaccination/boosting arm of research, we seek to recruit 200 total male and female participants who are Black/African-American or White/Caucasian. Participants must have received a SARS-CoV-2 vaccination booster within the past 24 hours to be enrolled. We aim to recruit a one-half African American sample ( $N = 100$ ), and a one-half White sample ( $N = 100$ ), both of which will be one-third to one-half male.

For the Set-Aside portion of the study: We will recruit 400 rural participants: 200 each from Arkansas and northern Michigan. Arkansas recruitment will be led by [name]. Arkansas inclusion criteria are resident African American, 18 years and over, and recruited from selected Arkansas rural counties and zip codes. Northern Michigan inclusion criteria are White American, 18 years and over, and recruited from counties considered rural based on the Economic Research Services' rural-urban continuum codes. In both recruitment locations, we will measure but not exclude based on prior SARS-CoV-2 natural infection and vaccination.

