**12. \* Will your research likely require non-exempt (expedited or full board) review?** 

Yes  No

**\* (1) Describe the criteria for who will be included or excluded from the study, including how subjects will be screened for eligibility.**

The formal inclusion criteria broadly encompass Flint area community members who are Black/African-American or White/Caucasian, 18 years and above, and enrolled in the Flint Registry. We will exclude participants who do not meet age or race criteria. Although we will not intentionally exclude them, our sample will include individuals from the Flint community who have ready access to interest – the primary mode of enrolling in the Flint Registry.

For the Set-Aside portion of the study: We will recruit 400 rural participants: 200 each from Arkansas and northern Michigan. Arkansas inclusion criteria are resident African American, 18 years and over, and recruited from selected Arkansas rural counties and zip codes. Northern Michigan inclusion criteria are White American, 18 years and over, and recruited from counties considered rural based on the Economic Research Services' rural-urban continuum codes. In both recruitment locations, we will measure but not exclude based on prior SARS-CoV-2 natural infection and vaccination. We will exclude participants who do not meet age or race criteria.

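### The two rural sites coincide with race and state, but the SAP's primary arm comparisons have no site term and no by-site estimate; adding both is a nearly free improvement

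*SAP*

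**What the plan says.** The Set-Aside component is described in the Protocol, Additional Study Information, item 2 (subject population): "We will recruit 400 rural participants: 200 each from Arkansas and northern Michigan". The inclusion criteria in item 12 (1) tie each location to one race: "Arkansas inclusion criteria are resident African American, 18 years and over, and recruited from selected Arkansas rural counties and zip codes", and "Northern Michigan inclusion criteria are White American, 18 years and over".

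The SAP describes the arms as follows: "Our arms include rural residents who are assigned either to the general (group 1) or rural targeted (group 2) antibody video group". For interval-level outcomes it states: "The primary analysis for all self report study outcomes is based on assessing mean differences across the two study arms", using independent-samples t-tests and Cohen's d. For the kit outcomes: "For dichotomous (yes-no) outcomes related to accepting and completing the antibody test kit we conducted two group chi square goodness of fit tests".

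The closest it comes to site is: "Subsequent analyses will explore sociodemographic variables and individual differences, such as gender and rural identity, as potential moderators of group differences", followed by: "Future exploratory considerations will utilize hierarchical moderated multiple regression procedures". Site, state and race are not named anywhere in the SAP.

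**The concern.** The sample consists of two equal blocks fixed by recruitment. They differ in race and region, and block membership is known for every participant. The primary comparisons ignore it.

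This is neither a bias nor a false-positive problem if assignment is random. Two things are lost:

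- **Precision.** Any difference between the sites in the outcome stays in the error variance.
- **A view of each community.** The Protocol's brief description (item 3) sets the Set-Aside aim in terms of rural populations that differ by race and region. A single average cannot show whether the rural-targeted video works in both. Effects of 0.50 SD at one site and 0 at the other, for example, would be reported as 0.25 SD.

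**Working it through.** **Inputs from the documents.** The planned total is 200 + 200 = 400, with one race per site. There are two arms, and the tests carry no site term. The documents give no power calculation for the 400, so there is no planned power figure to reproduce.

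**Assumptions, because the documents are silent.** Allocation is 1:1 (200 per arm, 100 per arm per site). Tests are two-sided at 5%. The within-site SD is 1. The effect is 0.28 SD, which gives about 80% power with no site gap. D is the gap between site means in within-site SDs, taken as 0.2, 0.3 and 0.5.

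**Step 1: variance.** For a 50:50 mixture of sites the total variance is 1 + D²/4, which gives 1.01, 1.0225 and 1.0625.

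**Step 2: assignment not stratified by site.** The sample-equivalent loss is 1 − 1/(1 + D²/4). Power uses the noncentral t with 398 df and noncentrality 0.28/√[(1 + D²/4) × 2/200]. With site in the model the noncentrality is 0.28/√(2/200) = 2.80 with 397 df, and power is 79.8%. With D = 0, power is 79.8% with or without the site term.

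**Step 3: arms balanced within site.** The arm difference is then free of site variation, but the t-test still uses the inflated SD. Its critical value is in effect multiplied by √(1 + D²/4), which makes it slightly conservative.

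| D | Unstratified: loss | Unstratified: power | Balanced: test size | Balanced: power | Balanced: loss | Power with site term |
|---|---|---|---|---|---|---|
| 0.2 | 1% | 79.4% | 4.9% | 79.5% | 1% | 79.8% |
| 0.3 | 2% | 78.9% | 4.8% | 79.1% | 2% | 79.8% |
| 0.5 | 6% | 77.3% | 4.3% | 78.0% | 4% | 79.8% |

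Simulation at D = 0.5 (20,000 trials per setting) agrees. The unstratified t-test has size 4.9% and power 77.3%. The balanced t-test has size 4.4% and power 78.2%; with site added, size is 5.0% and power 79.9%.

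**Step 4: kit outcomes**, if the chi-square test compares two proportions. Loss = 1 − mean[p(1−p)]/[p̄(1−p̄)].

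- Assumed site rates of 45% and 55%: 1 − 0.2475/0.25 = 1%.
- Assumed site rates of 40% and 60%: 1 − 0.24/0.25 = 4%.

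The 95% CI half-widths for the risk difference at 40% and 60% are:

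- unadjusted: 1.96√(2 × 0.25/200) = 9.8 points;
- site-stratified: 1.96√(2 × 0.24/200) = 9.6 points;
- one site alone: 1.96√(2 × 0.24/100) = 13.6 points.

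**Step 5: what by-site results can show.**

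- Half-width of a mean difference in one site: 1.97√(2/100) = 0.28 SD, against 1.97√(2/200) = 0.20 SD pooled.
- Power in one site alone (198 df): 50% for 0.28 SD, and 80% only at about 0.40 SD.
- Arm-by-site interaction: SE = √(4/100) = 0.20. With 396 df, power is 80% only for a difference of 0.56 SD, and 59% for 0.44 SD (for example 0.50 at one site and 0.06 at the other).

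**The case against.** The strongest reply is that an unadjusted comparison is a legitimate primary analysis and the precision at stake is small: at most 2.5 power points over the range shown (79.8% − 77.3%), and 0.2 points of half-width for the kit outcomes. Every magnitude rests on assumed inputs, and nothing in the documents shows that the sites differ on any outcome. That stands, and precision alone would be a weak reason to change the plan.

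Second, the SAP does not name the Set-Aside component, the two states or the number 400. The link rests on its reference to rural residents and a rural-targeted video, and pooling is inferred. This also stands, which is why the fix begins with a statement about pooling. If the sites are analysed separately, the by-site results already exist and only the combined estimate needs a site term.

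Third, the planned moderators are an open list. Race is an obvious sociodemographic variable and here equals site, so a moderated regression on race would carry both its main effect and its interaction with arm. This covers part of the gap for self-report outcomes. But neither race nor site is named, and the step is exploratory. It does not adjust the primary comparison, and no method is stated for the yes/no kit outcomes.

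Fourth, by-site estimates are noisy, and parts of the SAP are in the past tense, so the tests may already have been run. Both points limit how the additions should be labelled and read. Neither removes their descriptive value.

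**Conclusion.** The concern holds as an inexpensive improvement, not as an error that invalidates the analysis. With random assignment the planned tests are valid. Under the assumptions above, leaving site out costs the equivalent of about 1% to 6% of the sample for site gaps of 0.2 to 0.5 SD, and 1% to 4% for the assumed kit rates. The larger gain is descriptive: readers would see the arm effect in each of the two communities that the Set-Aside component was designed to recruit. Those estimates will be imprecise, and because race and state are fully aliased by eligibility, no analysis of these data can separate them. The equal site sizes are recruitment targets, so achieved numbers may shift the figures slightly. Confidence is medium, since the pooling and the size of any site gap are not documented.

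**What to change.** 1. State whether the primary comparisons pool both sites.
2. Add site (here equivalent to race and state) to the primary comparisons. For self-report outcomes use a linear model with arm and site. For kit acceptance and completion use a Cochran-Mantel-Haenszel test with a site-stratified risk difference.
3. Report arm effects by site with 95% confidence intervals, for both outcome types, as descriptive results.
4. Name site among the planned moderators. Note that the interaction test reaches 80% power only for a difference of about 0.56 SD and cannot separate race from state, so a non-significant result is not read as equal effects.
5. Keep any tests already run. If results are known, label items 2 to 4 as additional, post hoc analyses.

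The cost is one residual degree of freedom out of 398 and a re-run of the models. Site follows from recruitment location, so no new data are needed.

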**3. \* Brief description:** 

African Americans were infected and died from SARS-CoV-2 more than any other racial group in United States, including cities such as Flint, MI. Yet, connections to inflammatory biological processes in COVID-19 disparities remains unknown. This study aims to identify and compare inflammation among those with and without confirmed SARS-CoV-2 infection via antibody testing & conduct cross-race comparisons of inflammatory factors. The main objective is to encourage understanding and uptake of antibody testing. The central hypothesis is that African Americans will be receptive to antibody testing when benefits and limitations are communicated in a culturally effective manner. We will provide an opportunity to engage in salivary antibody screening - a non-invasive route to antibody testing that is highly suited to disparities-oriented COVID-19 research.

For the Set-Aside portion of the study: Rural Americans are at greater risk of many COVID-19 outcomes, and these disparities are likely to endure given lower vaccination uptake in many rural communities. Better understanding and addressing these rural disparities could be aided by SARS-CoV-2 antibody testing. However, implementing antibody testing education and outreach is challenged by the racial and regional diversity of rural contexts, as well as skepticism towards COVID-19 testing and treatments in many rural communities. The proposed "set aside" research assembles two disparities-focused SeroNet U01 teams – Michigan State University and the University of Arkansas for Medical Sciences. Together, these teams will adapt and extend their existing SeroNet projects to consider whether video communication for diverse rural populations can effectively encourage understanding and uptake of SARS-CoV-2 antibody testing in rural contexts.

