**4. Identify if your project involves any of the following: (check all that apply)**

**Activities That May Require Additional MSU Reviews:** [?](#)

Biospecimens from humans (e.g. human blood, tissue, cell lines, buccal swab)

**Activities That May Utilize MSU Resources:** [?](#)

There are no items to display

**Activities That May Be Subject To Additional Federal Requirements:** [?](#)

Certificate of Confidentiality

Registration and/or reporting with clinicaltrials.gov (by you or the sponsor)

**Activities That May Be Subject To Additional Requirements Based On Recruitment:** [?](#)

There are no items to display

**Activities That May Be Subject To International Requirements:** [?](#)

There are no items to display

**5. \*** Is this a research study in which one or more human subjects are prospectively assigned to one or more interventions (which may include placebo or other control) to evaluate the effects of the interventions on biomedical or behavioral health-related outcomes? [?](#)

Yes  No

\* Please select one of the options below:

Other

**6. \*** Will any subject's insurance be billed as part of this project? [?](#)

Yes  No

**7. \*** Are you aware of any individual who has a financial interest which may create an organizational conflict of interest? See HRPP policy 10-1, Conflict of Interest, for definitions and additional information. [?](#)

Yes  No

**8. \*** Has any financial arrangement, including compensation, ownership interest, stock options, or other ownership interest, (e.g., compensation that is: explicitly greater for a favorable result; in the form of an equity interest in the sponsor of a covered study; or in the form of compensation tied to sales of the product, such as a royalty interest) been established whereby the value of compensation or ownership interest to investigators conducting the study could be influenced by the outcome of the study?

Yes  No

**9. \*** Do any investigators or research staff have a financial interest related to the research that has not otherwise been disclosed elsewhere in this submission?

Yes  No

**10. \*** Will the research be conducted outside the United States?

Yes  No

**11. \*** Will subjects be compensated for participation in the study (e.g. money, gift cards, coupons for free food)?

Yes  No

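### The kit outcomes are tested with a chi-square named as goodness of fit where a two-by-two test of independence is needed; secondarily, no rule governs an overall claim drawn from several unranked tests

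*SAP*

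**What the plan says.** The SAP is a single short section on the rural Set-Aside comparison of a general with a rural-targeted video.

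- **Kit outcomes:** "For dichotomous (yes-no) outcomes related to accepting and completing the antibody test kit we conducted two group chi square goodness of fit tests". No null proportions, denominators or effect measure are given.
- **Self-report outcomes:** "The primary analysis for all self report study outcomes is based on assessing mean differences across the two study arms". The method follows: "A series of independent samples t-tests were conducted for all interval level/self-report outcomes, which included Theory of Planned Behavior and rural-adapted anticipatory racism measures". Two sets of measures are named, but the number of scales is not.
- **Effect size:** "We also computed Cohen's d effect sizes to consider practical significance of pairwise differences". This covers the mean differences only.
- **What is set apart:** only the moderator work. "Future exploratory considerations will utilize hierarchical moderated multiple regression procedures".

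The kit outcomes carry no primary or secondary label. In the available text, neither document gives a single primary outcome, a significance level, a test order or a multiplicity rule.

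In the protocol, the Set-Aside aim under item 3 (Brief description) is to consider "whether video communication for diverse rural populations can effectively encourage understanding and uptake of SARS-CoV-2 antibody testing in rural contexts"; it does not rank the two parts. On size, item 2 (Describe the subject population) says: "We will recruit 400 rural participants: 200 each from Arkansas and northern Michigan". Neither an allocation ratio nor an allocation method is stated. Item 4 of Additional Study Information lists trial registration among the applicable requirements, but the SAP cites no registered outcome.

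**The concern.** A goodness-of-fit test compares counts in one set of categories with fixed expected proportions. For a two-arm yes/no outcome, its literal form takes the number of acceptors in each arm and asks whether they divide equally. It uses neither the number who declined nor the number assigned to each arm. If the arms differ in size, acceptor counts will differ even when the videos work equally well. If the arms are equal, the test gives the acceptor counts more variability than they have, and a real difference in uptake is easier to miss. Uptake is half of the stated aim, so the kit tests matter.

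The secondary concern is the step from several tests to one conclusion. Each t-test is primary, and two kit tests stand beside them. Nothing says which result, or which combination of results, would show that the targeted video worked. If any one significant result were taken as enough, the chance of a false claim would exceed the per-test level.

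**Working it through.** The plan states no figure that can be reproduced. The input from the documents is 400 rural participants. The assumptions are two-sided 0.05, the arm splits shown, and 50% acceptance where there is no effect.

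**A. Kit tests**

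Let x1 and x2 be the acceptors in the two arms. The literal test rejects when (x1 − x2)² / (x1 + x2) > 3.84. With about 200 acceptors in total, that means |x1 − x2| > 1.96 × √200 = 27.7.

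*Size, arm sizes fixed.* With no effect, x1 − x2 has mean (n1 − n2)/2 and SD √(400 × 0.25) = 10.

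- 200/200: mean 0, limit at 27.7/10 = 2.77 SD, size 0.6% (exact enumeration 0.57%).
- 210/190: mean 10, limit at (27.7 − 10)/10 = 1.77 SD, size 3.8% (exact 3.85%).
- 220/180: mean 20, limit at (27.7 − 20)/10 = 0.77 SD, size 22% (exact 22.03%). Nearly all of these rejections favour the larger arm.
- Two-by-two Pearson test: 5.10% at 200/200 and 5.06% at 220/180.

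*Size, averaged over simple 1:1 randomisation.* Arm sizes now vary, and each acceptor is equally likely to be in either arm. The SD of x1 − x2 becomes √200 = 14.1, and 27.7/14.1 = 1.96, so the size is about 5%. Exact enumeration gives 5.1%, 5.0% and 5.0% at acceptance of 20%, 50% and 80%.

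*Power at 43% versus 57%, 200/200.* Expected acceptors are 86 and 114, a difference of 28 with SD √(2 × 200 × 0.57 × 0.43) = 9.9.

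- Literal test: (28 − 27.7)/9.9 = 0.03, power 51%.
- Two-by-two test: the limit is 1.96 × 10 = 19.6; (28 − 19.6)/9.9 = 0.85, power 80%.

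On the expected counts, the statistics are 28²/200 = 3.92 and 400 × (114² − 86²)²/200⁴ = 7.84, so the literal test halves the chi-square.

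Simple randomisation does not recover this loss. Each participant then contributes variance 0.5 − 0.07² = 0.4951, so the SD is √(400 × 0.4951) = 14.07. Then (28 − 27.7)/14.07 = 0.02, and power is again 51%. Enumeration over the random arm sizes confirms 51% against 80%.

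**B. Any-one-significant claims**

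For m independent tests, the chance of at least one false positive favouring the targeted video is 1 − 0.975^m; in either direction it is 1 − 0.95^m. For equal correlation between tests, the figures come from numerical integration of a one-factor normal model with critical value 1.96. Every test is taken to have its nominal size.

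| Tests | Favouring targeted video, correlation 0 / 0.5 / 0.9 | Either direction |
|---|---|---|
| 1 | 2.5% | 5% |
| 2 | 4.9 / 4.5 / 3.5% | 9.8 / 9.1 / 7.0% |
| 4 | 9.6 / 7.8 / 4.7% | 18.5 / 15.6 / 9.4% |
| 8 | 18.3 / 12.5 / 6.0% | 33.7 / 25.0 / 11.9% |

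Two tests stand for the two named self-report measures, four add the two kit outcomes, and eight allow for more scales. With Holm over four tests (first step 0.05/4 = 0.0125) and no true differences, the either-direction rate is 4.9 / 4.3 / 2.6%.

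**C. Cost of Holm**

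At 200/200, detectable d at 80% power = (z + 0.842) × √(1/200 + 1/200). This gives 0.28 at alpha 0.05 and 0.33 at 0.0125. Power at d = 0.28 falls from 80% to 62% at that strictest step.

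**The case against.** **The label may be loose wording.** Describing the chi-square as two-group suggests that an arm-by-outcome table may have been analysed and misnamed. A reader might infer that the kit p-values are wrong. The documents do not show that; they show only that the named test is unsuitable if it was done as named.

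**The literal test is not invalid under every design.** Averaged over simple 1:1 randomisation it keeps about 5%. The 22% belongs to one fixed split; a split at least that uneven arises in about 5% of simple 1:1 randomisations of 400, and 210/190 gives less than 5%. This stands, so the size figures are conditional. The loss of power applies both at 200/200 and averaged over simple randomisation.

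**The SAP makes no overall claim.** It plans outcome-by-outcome tests with effect sizes, and a difference reported only for its own outcome carries per-test error. The aim could also be read as requiring both understanding and uptake, in which case any-one-hit inflation does not arise. Both points stand and make the second part conditional.

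**Direction matters.** The either-direction rates include results favouring the general video, which could not support a claim for the targeted one. In the favourable direction two tests stay below 5%, though above the 2.5% of a single test.

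**The registration may name a primary outcome.** It was not available, so this cannot be excluded. Choosing a Holm family after the tests were run is also open to argument, since that choice is itself post hoc.

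**Conclusion.** The concern holds in two parts of unequal weight.

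The main part is the kit test. As named, it does not use the information that a two-arm yes/no comparison needs. Under the assumed rates, replacing it raises power from 51% to 80% and removes the dependence on the arm split (size from 0.6% to 22% over the splits shown). This rests on the literal reading; if a two-by-two test was in fact run, only the wording needs changing.

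The second part is narrower. A claim of overall success based on any one significant result would not be held at the per-test level. In the favourable direction the scenarios run from 3.5% to 18.3%, against 2.5% for one test. They are illustrations, because alpha, the number of tests and their correlation are not given.

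Two stronger inferences are not supported. A reader might conclude that the trial has an inflated error rate, but the SAP states no overall claim to which such a rate would apply. A reader might also combine the two parts into one error rate by treating the kit tests as independent. If a kit must be accepted before it is completed, as is natural, the two outcomes are closely linked and that combination fails.

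**What to change.** 1. **Kit outcomes.** Compute both p-values from a two-by-two test of independence (arm by yes/no) on all assigned participants, stating how those with no recorded answer are counted. Report each risk difference with a 95% CI. If this was already done, correct the test's name in the SAP. The cost is a recalculation from existing data.
2. **Overall claim.** State alpha and list every between-arm test. If a primary outcome was documented before the analysis, for example in the registration, cite it and test it at 5%. If not, limit conclusions to each named outcome, or show Holm-adjusted p-values beside the unadjusted ones for any overall claim and disclose the family as post hoc.

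The second item needs no new data. Its downside is the loss of sensitivity per outcome under Holm shown in part C of the working. Disclosure does not undo the fact that the family would be chosen after the tests were run.

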## Additional Study Information

**1. \* Describe the research procedures that involve obtaining information or biospecimens about a living person through interaction or intervention and/or by obtaining their identifiable private information or identifiable biospecimens. If subjects will participate in or undergo an intervention, fully describe the intervention. **

Human subjects in the proposed research will be engaged in an experimental study involving exposure to either standard (i.e., generally applicable) or culturally-targeted

informational videos materials about salivary testing for SARS-CoV-2 antibody. These brief videos in conjunction with the survey questions will be distributed via Qualtrics to the Flint community. The Flint Registry will provide contact information and demographics of eligible subjects to the SeroNet team. The SeroNet team will be recruiting participants via email/phone/mail. In collaboration with leading salivary bioscience experts, we will also furnish an opportunity to engage in salivary antibody screening – a non-invasive route to SARS-CoV-2 antibody testing that is highly suited to disparities-oriented COVID-19 research. Video materials will be developed in collaboration with clinical and community advisory committees that are highly suited to the proposed research, and we will present materials as professionally prepared online modules. Participants will also have the option to complete a spit kit in which their collected saliva will be used to enable assays for a dozen salivary cytokines, which we will link to antibody status.

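### The SAP names a chi-square goodness-of-fit test for the two-arm comparison of kit acceptance and completion; a 2x2 test of independence is needed

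*SAP*

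**What the plan says.** The SAP is a single short section. It defines the comparison: "Our arms include rural residents who are assigned either to the general (group 1) or rural targeted (group 2) antibody video group". For the continuous measures it uses a between-arm test: "A series of independent samples t-tests were conducted for all interval level/self-report outcomes". For accepting and completing the kit, the whole of the stated analysis is: "For dichotomous (yes-no) outcomes related to accepting and completing the antibody test kit we conducted two group chi square goodness of fit tests".

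The SAP gives no reference proportions, expected counts, table layout, degrees of freedom or significance level for these outcomes. It attaches the term primary analysis to the self-report outcomes and does not rank the kit outcomes.

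The protocol names no test. Its brief description says the rural study asks whether video communication "can effectively encourage understanding and uptake of SARS-CoV-2 antibody testing in rural contexts". Its description of the subject population gives the sample size by state, not by video arm: "We will recruit 400 rural participants: 200 each from Arkansas and northern Michigan". Neither document states an allocation ratio.

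**The concern.** A goodness-of-fit test asks whether one set of counts agrees with proportions specified beforehand. The question here is whether two independent arms have the same probability of a yes. That calls for a test of independence (equivalently, homogeneity) on the 2x2 table of arm by yes/no. The named test does not answer the stated question, and the proportions it would need are missing.

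Kit acceptance and completion are the yes/no outcomes closest to the uptake that the rural study aims to encourage, and this sentence is their only analysis. The SAP is written in the past tense, so results may already exist, and a reader cannot tell from the text which calculation produced them. A literal goodness-of-fit test could hide a real difference or declare a false one, depending on how it was set up and on the arm sizes.

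**Working it through.** The plan gives no figure to reproduce for these outcomes. The check asks how far each literal reading would depart from the 2x2 test.

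**Inputs**
- From the documents: two independent arms (SAP) and 400 rural participants in total (protocol, subject population).
- Assumed, because not stated: arm sizes of 200:200, 205:195, 210:190 and 220:180; a common uptake of 10% to 80%; a two-sided 5% level, so rejection above 3.841 on 1 df; no continuity correction.

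**Statistics**, with x1 and x2 the yes-counts in arms of size n1 and n2, and p the pooled rate (x1 + x2)/(n1 + n2):
- Pearson 2x2: (x1/n1 − x2/n2)² / [p(1 − p)(1/n1 + 1/n2)].
- Reading (a), yes-counts fitted to 50:50: (x1 − x2)² / (x1 + x2).
- Reading (b), one arm's counts fitted to the other arm's observed rate as if it were known.

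**Type I error**, by exact enumeration of all pairs of binomial outcomes:

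| Arms | (a) at 10% uptake | (a) at 50% | (a) at 80% |
|---|---|---|---|
| 200:200 | 3.8% | 0.6% | under 0.01% |
| 205:195 | 4.1% | 1.2% | 0.04% |
| 210:190 | 4.9% | 3.8% | 0.9% |
| 220:180 | 8.3% | 22% | 35% |

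Reading (b) gives 16.6% to 17.7% at 200:200. At 220:180 it gives 14.7% to 16.2% when the smaller arm is tested against the larger arm's rate, and 19.0% to 19.8% the other way round. Pearson 2x2 gives 4.8% to 5.3% throughout.

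**Why reading (a) goes both ways.** Take 50% uptake.
- Equal arms: x1 − x2 has variance 400 × 0.5 × 0.5 = 100, but the statistic divides by about 400 × 0.5 = 200. The test is therefore too cautious.
- At 220:180, x1 − x2 has mean (220 − 180) × 0.5 = 20 and standard deviation √100 = 10. Rejection needs a difference of about 1.96 × √200 = 27.7. The chance is P(Z > (27.7 − 20)/10) = P(Z > 0.77), about 22%, which matches the enumeration.

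**Check on reading (b).** The normal approximation is 2P(Z > 1.96/√(1 + n_tested/n_reference)). It gives 16.6% at 200:200, and 14.6% and 18.9% at 220:180.

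**Two hypothetical examples**
- Identical 70% uptake, 154/220 vs 126/180. Reading (a): 28²/280 = 2.80, p = 0.094. Pearson 2x2: 0, p = 1.0.
- 120/200 vs 150/200. Reading (a): 30²/270 = 3.33, p = 0.068. Pearson 2x2: 0.15² / [0.675 × 0.325 × (2/200)] = 10.256, p = 0.0014.

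**The case against.** The strongest reply is that this is a slip of terminology. A literal goodness-of-fit test has one sample, so describing it as a two-group test already points to a 2x2 test. The adjoining t-tests compare the same two arms, and no null proportion is given. This reading is plausible. If it is right, the p-values are unaffected and only the wording needs correcting. No part of the documents shows that a literal test was run.

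The largest figures also come from particular scenarios:
- A split at least as uneven as 220:180 has a probability of about 5.1% under simple 1:1 randomisation of 400 people, itself an assumption. Averaged over all such splits, reading (a) has a type I error of 4.9% to 5.0%, so its error depends on the split that occurred.
- Fitting the yes-counts to the allocation ratio instead of 50:50 removes the inflation. It remains conservative at every split examined (at 220:180: 3.8% at 10% uptake and 0.6% at 50%). The inflation under reading (a) therefore belongs to the 50:50 null, not to every goodness-of-fit test on the yes-counts.
- Nothing in the SAP points specifically to reading (b).

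Finally, no document makes the kit outcomes primary. The protocol's description of the video intervention under Additional Study Information concerns the Flint component, so its silence on allocation says little about the rural arms.

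These points limit how much weight the figures can bear. They do not make the named test correct, and they do not let a reader confirm which test was used.

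**Conclusion.** The concern holds. The test named for kit acceptance and completion is wrong as written, and the documents cannot settle whether the fault lies in the wording alone or also in the calculation. If a 2x2 test was run, there is no numerical error. If a literal goodness-of-fit test was run, the results could mislead in either direction, and the direction cannot be known without the arm sizes and the null proportions used. The range shown, from under 0.01% to 35% against a nominal 5%, rests on assumed arm sizes, uptake rates and significance level. It illustrates the risk and is not evidence against any reported p-value. This should be fixed: the error in the text is definite, its numerical consequence is uncertain, and the remedy is cheap.

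**What to change.** In the SAP sentence on dichotomous outcomes, replace the named test with: Pearson chi-square test of independence on the 2x2 table (arm by yes/no). Confirm from the analysis code or output which test was run. If it was the 2x2 test, the matter closes as a wording correction. If it was a literal goodness-of-fit test, recompute the acceptance and completion p-values from the 2x2 tables.

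The cost is one phrase and one check of the code or output. A re-run, on data already held, is needed only in the second case.
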